10.3.2.3. Overall Survival

Overall survival is defined as the time from randomization to death due to any cause. Patients not known to have died at the time of analysis will be right censored on the date at which they were last known to be alive before the analysis data cutoff date for the purposes of analysis.

Three interim and 1 final efficacy analyses of overall survival are planned. The first interim analysis will be performed at a 0.001 significance level at the time of the single MFS analysis. The number and percentage of death events in each treatment group will be summarized, along with Kaplan-Meier curves with the hazard ratio and its 95% CI. Two additional interim analyses and a final analysis of overall survival are planned after approximately 285, 440, and 596 deaths occur, respectively. The overall survival analyses will be performed using a stratified log-rank test to compare the 2 treatment groups. Depending on the outcome of time to PSA progression and time to first use of new antineoplastic therapy endpoints, the total type I error rate across the interim and final analyses will be controlled at 0.03 or 0.05 with the O'Brien-Fleming alpha spending function.¹⁴ The significance level will be fixed at 0.001 for the first interim analysis. For the other overall survival analyses, the significance levels will be recalculated based on the actual number of events at each analysis using the O'Brien-Fleming method, using the

remaining type I error rate (0.029 or 0.049 depending on the outcome of time to PSA progression and time to first use of new antineoplastic therapy endpoints). If an interim analysis of overall survival is statistically significant, it will be reported as the final analysis and no subsequent analyses will be performed. The approximate number of events and corresponding significance level at each analysis based on this methodology are provided in Table 11. The interim analysis testing methodology will be described in detail in the statistical analysis plan.

Table 11. Type I Error Spending for the Overall Survival Analyses

Analysis	Number of Death Events [1]	Significance Level	
		Error Rate: 0.03 [2]	Error Rate: 0.05 [3]
First interim	135	0.001	0.001
Second interim	285	0.001	0.002
Third interim	440	0.009	0.018
Final	596	0.026	0.044

1. Approximate number of targeted events.

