5. SAMPLE SIZE CONSIDERATIONS

The following assumptions are used in determining the sample size calculation for the MFS endpoint:

- 2:1 enzalutamide to placebo treatment allocation;
- An increasing nonuniform accrual of 0.25 patients per month per site with maximum accrual of 63 patients per month;
- For MFS a target hazard ratio of 0.72 at a 2-sided significance level of 0.05 with 90% power. Under an exponential model assumption, the target difference in Kaplan-Meier estimated median is 9 months (24 months versus 33 months). The median MFS of 24 months for the placebo group is based on published data.²

A total of 440 events provide 90% power to detect a target hazard ratio of 0.72 based on a 2-sided log-rank test and the overall significance level of 0.05. A sample size of approximately 1305 patients (870 enzalutamide and 435 placebo) will achieve 440 events. Approximately 10% of patients enrolled are expected to be lost to follow-up, will be found to have metastatic disease at study entry, or will have events censored due to required analytical methods, so approximately 1440 patients (960 enzalutamide and 480 placebo) will be enrolled. The time from date of first randomization until 440 MFS events are observed is estimated to be approximately 43 months.

Approximately 500 PSA progression events are expected at the time of the single MFS analysis. Based on a hazard ratio assumption of 0.60, this endpoint will have >95% power at a 2-sided significance level of 0.02 (see [Section 9.7.1](#) for details on multiplicity adjustments on key secondary endpoints).

Approximately 360 new antineoplastic therapy events are expected at the time of the single MFS analysis. This endpoint will have 80% power to detect a hazard ratio of 0.70 at a 2-sided significance level of 0.02 (see [Section 9.7.1](#) for details on multiplicity adjustments on key secondary endpoints).

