The study is also powered for OS. Specifically, 590 death events will be required to have 85% power to detect a hazard ratio of 0.77 at a 2-sided significance level of 0.05. Under an exponential model assumption, the target difference in Kaplan-Meier estimated medians is 13.7 months (46 months vs. 59.7 months). If either time to PSA progression or time to new antineoplastic therapy endpoint fails to show significance, OS will be tested at a 2-sided significance level of 0.03. Under this scenario, 590 death events will provide ~79% power to detect a hazard ratio of 0.77 (see [Section 9.7.1](#) for details on multiplicity adjustments on key secondary endpoints).

The sample size and power calculations were performed using the software package East 5.4 (Cytel Inc., Cambridge, MA).

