A stratified log-rank test will be used to compare the treatment groups with the same strata as in the time to MFS analysis described in [Section 9.7.2](#).

At the time of the third interim and at the final analysis of OS, this endpoint will be updated and provided as an exploratory analysis.

Overall Survival

OS is defined as the time from randomization to death from any cause. For patients who are alive at the time of the analysis data cutoff, OS time will be censored at the last date the patient was known to be alive or analysis data cutoff date, whichever is earlier. Patients with no postbaseline survival information will be censored on the date of randomization.

As step 4 of the testing strategy described in [Section 9.7.1](#), the ITT analysis for the OS endpoint will be conducted with 0.05 (or 0.03 if either time to PSA progression or time to new antineoplastic therapy fails to show significance) alpha level (2-sided), if and only if, enzalutamide is assessed to be statistically superior to placebo for the primary endpoint of MFS. Three interim analyses and 1 final analysis for OS are planned. The data cutoff date will be applied to achieve the approximate number of deaths at each of these analyses.

Depending on the outcome of the time to first use of new antineoplastic therapy endpoint, the total type I error rate across the interim and final analyses will be controlled at 0.03 or 0.05 with the O'Brien-Fleming alpha spending function. The significance level will be fixed at

0.001 for the first interim analysis. For the other overall survival analyses, the significance levels will be recalculated based on the actual number of events at each analysis using the O'Brien-Fleming method, using the remaining type I error rate (0.029 or 0.049 depending on the outcome of the time to PSA progression and time to first use of new antineoplastic therapy endpoint). If an interim analysis of overall survival is statistically significant, it will be reported as the final analysis and no subsequent analyses will be performed. The approximate number of events and corresponding significance level at each analysis based on this methodology are provided in Table 4.

Table 4: Type I Error Spending for the Overall Survival Analyses

Analysis	Number of Death Events [1]	Significance Level	
		Error Rate: 0.03 [2]	Error Rate: 0.05 [3]
First interim	135	0.001	0.001
Second interim	285	0.001	0.002
Third interim	440	0.009	0.018
Final	596	0.026	0.044

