[1] Approximate number of targeted events.

[2] Will be used if either time to PSA progression or time to first use of new antineoplastic therapy endpoint fails to show significance. The significance level will be fixed at 0.001 for the first interim analysis. For the other analyses, the significance levels will be recalculated based on the actual number of events at each analysis using the O'Brien-Fleming method.³

[3] Will be used if both time to PSA progression and time to first use of new antineoplastic therapy endpoint show significance. The significance level will be fixed at 0.001 for the first interim analysis. For the other analyses, the significance levels will be recalculated based on the actual number of events at each analysis using the O'Brien-Fleming method.³

The first interim analysis will be conducted at a 0.001 significance level at the time of the primary MFS analysis. A stratified log-rank test will be used to compare the 2 treatment groups. The number and percentage of death events in each treatment group will be summarized with Kaplan-Meier curves of overall survival with the hazard ratio and its 95% CI.

A second interim analysis is planned after approximately 285 death events are observed. A stratified log-rank test will be used to compare the 2 treatment groups at a 0.002 or 0.001 (depending on the outcome of time to PSA progression and time to new antineoplastic therapy tests) significance level (exact significance level will be calculated based on exact number of events using the O'Brien-Fleming alpha spending function). The number and percentage of death events in each treatment group will be summarized with Kaplan-Meier curves of overall survival with the hazard ratio and its 95% CI.

A third interim analysis is planned after approximately 440 death events are observed. A stratified log-rank test will be used to compare the 2 treatment groups at a 0.018 or 0.009 (depending on the outcome of time to PSA progression and time to new antineoplastic

therapy tests) significance level (exact significance level for this analysis will be calculated based on exact number of events using the O'Brien-Fleming alpha spending function). The number and percentage of death events in each treatment group will be summarized with Kaplan-Meier curves of overall survival with the hazard ratio and its 95% CI.

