The final analysis is planned after approximately 596 death events are observed. A stratified log-rank test will be used to compare the 2 treatment groups at a 0.044 or 0.026 (depending on the outcome of time to PSA progression and time to new antineoplastic therapy tests) significance level (exact significance level for this analysis will be calculated using the O'Brien-Fleming alpha spending function). The number and percentage of death events in each treatment group will be summarized with Kaplan-Meier curves of overall survival with the hazard ratio and its 95% CI. If an interim OS analysis is statistically significant, it will be reported as the final analysis and no subsequent analyses will be performed.

At the time of the final analysis of OS, subgroup analyses will be conducted using the same analysis methods as for the subgroup analyses of MFS described in Section 9.7.2.

At the final analysis of OS, to adjust the treatment crossover effect, a sensitivity analysis of OS using Rank-Preserving Structural Failure Time Model (RPSFTM) method will be performed. Additionally, the inverse probability of treatment weighting (IPTW) method may also be performed as an exploratory analysis as appropriate.

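### Overall survival is tested at group-sequential levels, but each look reports an unadjusted 95% CI and hazard ratio, which at the interims can disagree with the test

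*SAP*

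**What the plan says.** SAP 9.7.3 plans three interim analyses and one final analysis of OS. Table 4 gives two columns of two-sided levels. The 0.05 column applies if time to PSA progression and time to new antineoplastic therapy are both significant; otherwise the 0.03 column applies.

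The text repeats these levels look by look. At the third interim, "A stratified log-rank test will be used to compare the 2 treatment groups at a 0.018 or 0.009" level; at the final, "A stratified log-rank test will be used to compare the 2 treatment groups at a 0.044 or 0.026" level. For each of the four looks a separate sentence says that the death counts "will be summarized with Kaplan-Meier curves of overall survival with the hazard ratio and its 95% CI". Protocol 10.3.2.3 says the same of the first interim: "along with Kaplan-Meier curves with the hazard ratio and its 95% CI".

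On stopping, SAP 9.7.3 says: "If an interim analysis of overall survival is statistically significant, it will be reported as the final analysis and no subsequent analyses will be performed".

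Neither document mentions a repeated, level-matched or stopping-adjusted interval, or a bias-adjusted HR. Nor is this CI called descriptive. SAP 9.7.1 and 9.7.4 do use the labels exploratory and descriptive, but for other analyses; OS is a formally tested key secondary endpoint.

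**The concern.** A conventional 95% CI corresponds to a two-sided 0.05 test. Beside a test at 0.001, 0.002 or 0.018, it gives the reader a second and much looser criterion. An interim can then be reported as not significant with an interval that excludes 1.

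There is also an estimation problem. A trial that stops because a boundary is crossed has been selected partly on a favourable fluctuation. The naive HR is then too far from 1 on average, and the naive interval need not have its stated coverage. Because a significant interim is reported as final, those would be the lasting OS estimate and interval. MFS has neither problem: it is analysed once, at 0.05.

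**Working it through.** **Inputs.** Allocation: "2:1 enzalutamide to placebo treatment allocation" (SAP 5), so one death carries 2/3 × 1/3 = 2/9 units of information on the log HR. Deaths and levels: SAP Table 4. Design HR: 0.77 (SAP 5).

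**1. Reproduce the plan's figures.** SAP 5 states: "590 death events will be required to have 85% power to detect a hazard ratio of 0.77 at a 2-sided significance level of 0.05". Deaths = (1.960 + 1.036)² / [(2/9) × (ln 0.77)²] = 8.978 / 0.01518 = 591.4, or 592, against 590. Power at 590 deaths: √(590 × 0.01518) = 2.993; Φ(2.993 − 1.960) = 0.849 at level 0.05 and Φ(2.993 − 2.170) = 0.795 at level 0.03. The second agrees with "590 death events will provide ~79% power to detect a hazard ratio of 0.77".

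O'Brien-Fleming-type spending of the remaining 0.049 at 285, 440 and 596 deaths gives 0.0023, 0.0170 and 0.0435. Spending 0.029 gives 0.0008, 0.0086 and 0.0262. These match Table 4 to three decimals, except 0.017 against the printed 0.018, which does not affect this point.

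**2. Where interval and test disagree.** The standard error of the log HR is 1/√(2d/9), with d the number of deaths. The test rejects when the HR is at or below exp(−z × SE), with z taken from the look's level. The 95% CI excludes 1 when the HR is below exp(−1.960 × SE).

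| Deaths | SE | CI excludes 1 below | Test rejects at or below, 0.05 column (z) | Test rejects at or below, 0.03 column (z) |
|---|---|---|---|---|
| 135 | 0.183 | 0.699 | 0.548 (3.291) | 0.548 (3.291) |
| 285 | 0.126 | 0.782 | 0.678 (3.090) | 0.661 (3.291) |
| 440 | 0.101 | 0.820 | 0.787 (2.366) | 0.768 (2.612) |
| 596 | 0.087 | 0.843 | 0.839 (2.014) | 0.824 (2.226) |

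Between the two limits, the interval excludes 1 and the test fails.

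**3. How often, at HR 0.77.** Look 1 can be done by hand. The mean of Z is 0.2614 / 0.1826 = 1.432, so the chance is Φ(3.291 − 1.432) − Φ(1.960 − 1.432) = 0.968 − 0.701 = 0.267. Later looks need the joint distribution: 2 million simulated paths with independent increments, stopping at the printed levels.

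| Chance of reaching the look, CI excluding 1, test failing | Look 1 | Look 2 | Look 3 | Final | At least one look |
|---|---|---|---|---|---|
| 0.05 column | 27% | 38% | 14% | 1% | 61% |
| 0.03 column | 27% | 42% | 24% | 7% | 69% |

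If the true HR is 1, the chance for at least one look is 10.5% or 11.8%.

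**4. Coverage and estimate at the stopping look** (same simulation, 0.05 / 0.03 column).

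| Quantity | Result |
|---|---|
| HR 0.77: whole-design coverage | 93.2% / 93.1% |
| HR 0.77: mean reported HR, whole design | about 0.75 in both |
| HR 0.77: chance of an early stop | 59% / 49% |
| HR 0.77: coverage given an early stop | 92.7% / 91.0% |
| HR 0.77: stop at look 1 | 21% / 21% |
| HR 0.77: stop at look 2 | 88% / 83%, mean HR about 0.64 / 0.63 |
| HR 0.77: stop at look 3 | 99.5% / 99.0% |
| HR 0.85: coverage given an early stop | 82% / 74% |
| HR 0.70: coverage given an early stop | 96.1% / 95.8% |
| HR 0.65: coverage given an early stop | 97.0% / 96.9% |

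**The case against.** The CI decides nothing. SAP Table 3 makes the stratified log-rank p-value the criterion, Table 4 prints the level, and the CI stands in a separate summary sentence beside counts and curves. A reader might infer that the overall error rate is inflated. It is not: the printed levels give about 0.05 and 0.03 overall. This stands, and it confines the point to reporting.

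A reader might also infer that coverage is below 95% whenever OS stops early. That does not hold. At HR 0.77, 72% (0.05 column) or 75% (0.03 column) of early stops come at look 3, where coverage is about 99%. At HR 0.65 to 0.70, coverage after an early stop is about 96–97%.

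Much of the average shortfall at HR 0.77 comes from look 1, which was probably already past. SAP 2 says MFS was met at the 28 June 2017 cutoff, the first OS interim belongs to that analysis, and the protocol's open-label supplement still plans the later looks. That look 1 did not cross is an inference; no OS result is given. Given that look 2 is reached, early stops at HR 0.77 have coverage of about 96.8% (0.05 column) or 95.8% (0.03 column). What survives is the disagreement at looks 2 and 3, the result of a stop at look 2, and under-coverage for weaker effects.

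Finally, a reader might infer that sites and patients would see these interim OS estimates after unblinding. The documents describe unblinding of patients; they do not say that interim OS results are released.

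**Conclusion.** The point holds as a minor reporting and estimation weakness. The stated 95% is not matched to the OS test at the interims, no adjusted interval or estimate is planned, and a significant interim would be reported as final on that basis. At the design HR, disagreement between interval and test at some look is more likely than not (61% or 69%). It is concentrated at the interims; at the final look it is negligible in the 0.05 column and small in the 0.03 column.

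Coverage has to be stated by true HR and stopping look. It is moderately low on average at HR 0.77, lower for weaker effects, and at or above nominal for stronger effects and for look-3 stops. Only one column will apply, depending on the two earlier key secondary tests.

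These figures assume proportional hazards, a normal approximation for the log HR, the planned death counts, the printed levels and a Wald-type CI consistent with the log-rank test. That the CI is unadjusted is inferred from the absence of any stated adjustment.

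**What to change.** In SAP 9.7.3:

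- At each OS look, report the HR with a repeated CI matched to the level actually applied. On the printed levels these are 99.9%, 99.8%, 98.2% and 95.6% in the 0.05 column, or 99.9%, 99.9%, 99.1% and 97.4% in the 0.03 column.
- For the OS analysis reported as final, add a stage-wise-ordering 95% CI and a median-unbiased HR. Matching the level removes the disagreement with the test but does not correct the estimate after early stopping.
- Keep the conventional 95% CI only if it is labelled descriptive and not adjusted for interim analyses.

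The tests, levels, data and patient numbers do not change. The work is SAP wording and standard group-sequential output. The downside is wider level-matched intervals. On the log scale the ratio is z/1.960: at look 2, 3.090/1.960 = 1.58 or 3.291/1.960 = 1.68; at look 3, 1.21 or 1.33; at the final, 1.03 or 1.14 (0.05 and 0.03 columns respectively).

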9.7.4. Analysis of Other Secondary Endpoints

The following analyses will be performed in the ITT population. The analyses and resulting p-values will be deemed descriptive; adjustments for multiplicity are not planned.

Time to Pain Progression

Pain will be assessed using the score from the BPI-SF question 3: "Please rate your pain by marking the box beside the number that best describes your pain at its worst in the last 24 hours." Time to this event is defined as the time from randomization to onset of pain progression, where pain progression is defined as a 2-point or more increase from baseline in the question 3 score. Patients without observed pain progression at the time of analysis will be right censored at the date of last pain assessment for the purposes of analysis. A stratified log-rank test will be used on the ITT population to compare the 2 treatment groups with the same strata as in the time to MFS analysis described in [Section 9.7.2](#).

Time to First Use of Cytotoxic Chemotherapy

Time to first use of cytotoxic chemotherapy is defined as the time from randomization to the first use of cytotoxic chemotherapy for prostate cancer. Patients not starting treatment with a cytotoxic chemotherapy for prostate cancer at the time of analysis will be right censored at the date of last assessment before the analysis data cutoff date for the purposes of analysis. A stratified log-rank test will be used on the ITT population to compare the 2 treatment groups with the same strata as in the time to MFS analysis described in [Section 9.7.2](#).

At the time of the third interim and at the final analysis of OS, this endpoint will be updated and provided as an exploratory analysis.

Chemotherapy-Free Disease-Specific Survival

Chemotherapy-free disease-specific survival is defined as the time from randomization to first use of cytotoxic chemotherapy for prostate cancer or death due to prostate cancer as assessed by the investigator. Patients not starting treatment with a cytotoxic chemotherapy or not known to have died due to prostate cancer at the time of analysis will be right censored at the date of last assessment before the analysis data cutoff date for the purposes of analysis. A stratified log-rank test will be used to compare the treatment groups with the same strata as in the time to MFS analysis described in [Section 9.7.2](#).

At the time of the third interim and at the final analysis of OS, this endpoint will be updated and provided as an exploratory analysis.

Chemotherapy-Free Survival

Chemotherapy-free survival is defined as the time from randomization to first use of cytotoxic chemotherapy for prostate cancer or death. Patients not starting treatment with a cytotoxic chemotherapy or not known to have died at the time of analysis will be censored at the date of last assessment before the analysis data cutoff date for the purposes of analysis. A stratified log-rank test will be used on the ITT population to compare the 2 treatment groups with the same strata as in the time to MFS analysis described in [Section 9.7.2](#).

At the time of the third interim and at the final analysis of OS, this endpoint will be updated and provided as an exploratory analysis.

Analysis of Brief Pain Inventory (BPI-SF)

The 4 individual items used to evaluate pain intensity are 'worst', 'least', 'average', and 'now' (current pain). Pain ratings range from 0 (zero) to 10 for each item. The mean pain severity score will be calculated using the 4 individual items. The 7 individual items used to evaluate pain interference include general activity, mood, walking ability, normal work, relations with other people, sleep, and enjoyment of life. Interference rating ranges from 0 (zero) to 10 for each item. BPI-SF pain interference will be scored as the mean of the 7 individual interference items. This mean can be used if more than 50% of the total items (4 of 7) have been completed at a given assessment. Descriptive statistics will be provided for the ITT population to summarize each individual item and the two domains scores (severity and interference) by treatment group. Missing data will be excluded from the analysis.

PSA Response

PSA response will be calculated at each visit as a decline from baseline in PSA (ng/mL) at the following maximal PSA response categories:

- Decline of $\geq 50\%$ will be response;

- Decline of $\geq 90\%$ will be response;
- Decline to undetectable level will be response.

Undetectable level is defined as below the limit of quantification of the centrally assessed PSA results. PSA response must be confirmed by a second consecutive value at least 3 weeks later. The percentage of patients in the ITT population with maximal PSA declines of at least 50%, 90%, and undetectable will each be compared between the 2 treatment groups using a stratified Cochran-Mantel-Haenszel mean score test with the same strata as in the time to MFS analysis described in [Section 9.7.2](#). Missing PSA value will be assigned to be nonresponder.

Analysis of Quality of Life

The Functional Assessment of Cancer Therapy – Prostate (FACT-P) is a multidimensional, self-reported, quality-of-life instrument specifically designed for use with prostate cancer. It consists of 27 core items that assess patient function in 4 domains: Physical, Social/Family, Emotional, and Functional wellbeing, which is further supplemented by 12 site-specific items to assess for prostate cancer symptoms. Each item is rated on a 0 to 4 Likert-type scale. The FACT-P domain scores and global score will be calculated using the Manual of Functional Assessment of Chronic Illness Therapy (FACIT) Measurement System⁵ and summarized for the ITT population along with their change from baseline by treatment group. Missing data will be excluded from the analysis.

The EQ-5D-5L questionnaire is a standardized instrument for use as a measure of health-related quality of life for men with prostate cancer. Patients will self-rate their current state of mobility, self-care, usual activities, pain/discomfort, and anxiety/depression on a 5-point categorical scale ranging from “no problem” to “extreme problem” within each dimension.

The EORTC QLQ-PR25, a module of the EORTC QLQ-30 questionnaire, was developed to assess the quality of life of patients with prostate cancer. Patients will self-rate their current state of pain as it relates to urination, ease and frequency of urination, and bowel and other problems during the past week. Patients will also answer 5 questions about weight loss/gain and sexual interest and 5 questions about sexual activity during the past 4 weeks. Patients will choose 1 of 4 possible responses that record level of intensity (not at all, a little, quite a bit, very much) within each dimension.

The number and percentage of patients with each response in each domain will be summarized descriptively by study visit for the ITT population for each treatment group. Missing data will be excluded from the analysis.

